8.2 NONINVESTIGATIONAL MEDICINAL PRODUCT(S)

The following classes of drugs are identified as non-IMP because the medication is a potential background therapy:

- Statins.
- Cholesterol absorption inhibitors (ezetimibe).
- Bile acid-binding sequestrants (such as cholestyramine, colestipol, colesvelam).
- Nicotinic acid.
- Fenofibrate.
- Omega-3 fatty acids (≥ 1000 mg daily).

8.3 BLINDING PROCEDURES

8.3.1 IMP

Not applicable, this study is an open-label design.

8.3.2 Lipid parameters

Lipid parameter values from blood samples obtained after the inclusion visit and during the main phase, run by the central lab, will not be communicated to the sites so that the patient's LDL-C values do not influence the Investigator's safety evaluation during the main treatment period for all cohorts and up to the end of the follow-up period for Cohorts 1-3.

During the open-label extension period, the lipid levels will be communicated to the investigator. The Investigator will be responsible, based on his/her own judgment related to the patients' LDL-C levels and the safety profile, to continue or discontinue alirocumab throughout the study. The reasons of any adjustment should be documented and recorded in the e-CRF.

8.3.3 Anti-alirocumab antibodies

Patients' anti-alirocumab antibody results will not be communicated to the sites, during the main phase, so that the patient's ADA levels do not influence the Investigator's safety evaluation during the main dose finding treatment period for all cohorts and up to the end of the follow-up period for Cohorts 1-3.

Patients who do not enter the extension phase or who prematurely discontinue the main phase and have a titer at or above 240 for anti-alirocumab antibody at the follow-up visit (for Cohorts 1-3) or at the end of the dose finding treatment period (for Cohort 4) will have additional antibody sample(s), at 6 to 12 months after the last dose and thereafter about every 3 to 6 months until titer returns below 240. Patients who enter the extension phase will be monitored for anti-alirocumab antibodies as per the study flowchart ([Section 1.4](#)).

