1 FLOW CHARTS

1.1 GRAPHICAL STUDY DESIGN (MAIN PHASE)

1.1.1 COHORTS 1 TO 3

[figure not shown]
1.1.2 COHORT 4

- * Inclusion (I): The inclusion or entry into the open-label dose finding treatment period for Cohort 4.
- ** The main phase for Cohort 4 will include 3 alirocumab injections (at W0, W4, and W8).
- *** For Cohort 4, the study duration includes an extended 12 week treatment period, including a Week 10 visit, but will not have a follow up period, in contrast to the study design for Cohorts 1, 2, and 3.
- **** Week 12 is the end of the open-label dose finding treatment period and possible entry point into the extension for Cohort 4.

[figure not shown]

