Visit Type		Clinical Site	Clinical Site	Phone Call	Clinical Site	Phone Call	Clinical Site	Clinical site ^a	Clinical Site
Treatment:									
Alirocumab Administration Q4W ^c			X		X		X		
Concomitant Medication		X	X	X	X	X	X	X	X
Review of diet ^d		X	X		X		X		X
Check of stability of background LMT		X	X	X	X	X	X		X
Efficacy:									
Total-C, calculated LDL-C, HDL-C, TG, non-HDL-C ^d		X	X		X		X	X	X
Apo B, Apo A-1, ratio Apo B / Apo A-1, and Lp(a) ^d		X	X				X		
Safety:									
AE /SAE recording (if any)		X	X	X	X	X	X	X	X
Vital Signs ^g		X	X		X		X		X

Main Phase Cohort 4	Screening Period (including run-in if applicable)	Open-Label Dose-finding Treatment Period							
		1	2	3	4	5	6	7	8
VISIT		1	2	3	4	5	6	7	8
Week (W)	Up to W-6	W0/D1 ^b	W2	W4	W6	W8	W10	W12	
Visit Window (+/- days)	+7		±3	±3	±3	±3	±7	±7	
Visit Type	Clinical Site	Clinical Site	Phone Call	Clinical Site	Phone Call	Clinical Site	Clinical Site ^a	Clinical Site	
Laboratory Testing ^d :									
heFH genotyping (Mandatory for consenting patients without documented heFH diagnosis; optional for documented heFH diagnosis patients wishing to undergo genotyping) ^e	X	X		X		X			
Hematology and chemistry ^f	X			X		X			
Creatine phosphokinase (CPK)	X			X		X			
Liver panel ^g	X			X		X			
Adrenal gland hormones ^h		X				X			
Gonadal and pituitary hormones ⁱ		X				X			
Fat soluble vitamins ^j		X				X			
Pregnancy test ^k	X	X				X			X
Anti-alirocumab antibodies (ADA) ^{l/m}		X				X			
PCSK9 levels (free and total)/serum alirocumab concentration (PK) ^l		X		X		X	X	X	X

a The Week 0, 4, 8, 10 and 12 visits will take place at the clinical site. For Week 2 and Week 6, a phone call may be done instead of a home or office visit.

b Two site visits may be needed to complete eligibility confirmation.

c The Week 0, 4 and 8 alirocumab injections will be administered at the clinical site by the site staff. Prior to each alirocumab administration, a local topical anesthetic may be utilized as per the Investigator, if at clinical site

- d Prior to any laboratory testing, the site may utilize a local topical anesthetic as per the Investigator. In case only a limited amount of blood can be drawn, specific tests performed for each sample obtained will be prioritized.

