- e Genotyping for heFH will be conducted from a specimen of whole blood, saliva, or buccal swab in patients consenting to undergo genotyping testing. This test will be recommended for all patients but will be mandatory only for patients without clinical diagnosis or no previous documented genotyping. In case of non-mandatory genotyping the sample could be taken preferentially during the screening period but could be done at any visit during the 8-week dose-finding part of the trial.
- f Hematology includes: complete blood cell count (CBC) including hematocrit, hemoglobin, red blood cell count, white blood cell count with differential count, and platelets. Chemistry includes: glucose, sodium, potassium, chloride, bicarbonate, calcium, phosphorous, urea nitrogen, creatinine, uric acid, lactate dehydrogenase (LDH), total protein, albumin, and γGT.
- g Liver panel: ALT, AST, alkaline phosphatase (ALP), and total bilirubin.
- h Adrenal gland hormones: cortisol (with reflexive ACTH levels if cortisol <LLN) and dehydroepiandrosterone sulfate (DHEAS).
- i Pituitary hormones: luteinizing hormone (LH) and follicle-stimulating hormone (FSH). Gonadal hormones: testosterone [males] and estradiol [females].
- j Fat soluble vitamins: A (retinol), D (25 hydroxy vitamin D), E (alpha-tocopherol), and K (phylloquinone).
- k Pregnancy test should be done on females of childbearing potential who are sexually active or females who have experienced menarche. The Screening (Week -2) pregnancy test should be a blood test. All other pregnancy tests will be with a local urine pregnancy test.
- l ADA and PK samples should be collected before alirocumab administration.
- m Only patients who prematurely discontinue the main phase or do not enter the optional extension phase and have a titer at or above 240 for ADA at follow-up visit will have additional ADA samples, at 6 to 12 months after the last alirocumab administration and thereafter, about every 3 to 6 months until titer returns below 240.
- n See [Appendix E](#) for Tanner stages evaluation.
- o Document prior medication history within the previous 12 weeks, especially for lipid modifying therapy (including statin) and nutraceutical products that may affect lipids (eg, omega-3 fatty acids, plant stanols such as found in Benecol, flax seed oil, psyllium).
- p Patients will be instructed to follow a diet in accordance with the American Academy of Pediatrics guidelines or equivalent throughout the entire study.

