9.3.1.1 Sampling time

Serum samples for anti- alirocumab antibody determination will be drawn periodically throughout the study as per schedule noted in the study flowchart of [Section 1.3](#) and [Section 1.4](#). All scheduled samples will be obtained before IMP injection (predose). Patients who prematurely discontinue the main phase or do not enter the optional extension phase, prematurely discontinue the extension phase or decide not to proceed to the Phase 3 study and who have a titer at or above 240 for anti- alirocumab antibody at follow-up visit (for Cohorts 1-3) / end of dose finding treatment period (Cohort 4) / end of extension phase will have additional antibody sample(s), at 6 to 12 months after the last dose and thereafter about every 3 to 6 months until titer returns below 240. The sponsor will notify the sites.

9.3.1.2 *Sampling procedure*

Detailed procedure of sample preparation, storage and shipment will be described in the specific laboratory manual which will be provided to sites. Five (5) mL blood volume is to be collected for each anti- alirocumab antibody sample.

9.3.1.3 *Bioanalytical method*

All anti- alirocumab antibody (ADA; anti-drug antibody) samples will be analyzed by the Regeneron Clinical Bioanalysis Group.

Anti- alirocumab antibody samples will be analyzed using a validated non-quantitative, titer-based bridging immunoassay. It involves an initial screen, a confirmation assay based on drug specificity, and a measurement of the titer of anti-alirocumab antibodies in the sample.

Samples that are positive in the ADA assay will be assessed for neutralizing antibodies using a validated, non-quantitative, competitive ligand binding assay (Bioanalytical Validation Report

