- Review patient's diet. Patient should be on a diet in accordance with the American Academy of Pediatrics guidelines ([1](#)) or equivalent.
- Perform physical examination.
- Get body weight measurement.
- Take vital signs including HR and BP.

- Urine pregnancy test (female who have experienced menarche only).
- Obtain fasting blood sample for:
 - Lipids: total-C, calculated LDL-C, HDL-C, TG, non-HDL-C, Apo B, Apo A-1, ratio Apo B/Apo A-1, and Lp(a),
 - Hematology: red blood cell count including hematocrit, hemoglobin, WBC count with differential count and platelets,
 - Chemistry: glucose, sodium, potassium, chloride, bicarbonate, calcium, phosphorous, urea nitrogen, creatinine, uric acid, total protein, LDH, albumin, and γ GT,
 - Liver panel (ALT, AST, ALP, and total bilirubin),
 - CPK,
 - Adrenal gland hormones: cortisol (with reflexive ACTH levels if cortisol <LLN), dehydroepiandrosterone sulfate (DHEAS),
 - Gonadal and pituitary hormones: testosterone (male) and estradiol (female), luteinizing hormone (LH), follicle-stimulating hormone (FSH),
 - Fat soluble vitamins: retinol (vitamin A), 25hydroxy-vitamin D (vitamin D), alpha-tocopherol (vitamin E), phylloquinone (vitamin K).
- Anti-alirocumab antibodies.
- Serum alirocumab concentration (PK).
- PCSK9 levels (free and total).
- Check of stability of background LMT.
- Reminder:
 - An appointment will be given for the next study site visit or phone call visit (first follow-up study visit).
- For Cohort 4, the final third injection of this period will take place at the study site

10.1.2.6 Visit 7/Week 10 (Day 70 \pm 7) at clinical site (Cohort 4 Only):

- Collect AEs.
- Record concomitant medication.
- Obtain fasting blood sample for:
 - Lipids: total-C, calculated LDL-C, HDL-C, TG, non-HDL-C.
 - PCSK9 levels (free and total) / Serum alirocumab concentration (PK).

10.1.2.7 Visit 8/Week 12 (end of the OL dose finding treatment period) (Cohort 4 only)

- Collect AEs.
- Record concomitant medication.
- Get body weight and height measurements.

- Assess Tanner stage.
- Take vital signs including HR and BP.
- IVRS/IWRS contact.
- Check of stability of background LMT.
- Urine pregnancy test (female who have experienced menarche only).
- Obtain fasting blood samples for:
 - Lipids: total-C, calculated LDL-C, HDL-C, TG, non-HDL-C.
 - PCSK9 levels (free and total) / Serum alirocumab concentration (PK).

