2.1.4.8 *Anti-alirocumab antibodies variables*

Anti-alirocumab antibodies (ADA) are assessed:

- At baseline (see [Section 2.1.1](#) for definition)
- During the OLDFI period at Week 8 or early termination and during follow-up (Week 16 for Cohorts 1& 2 or Week 14 for Cohort 3) and Week 12 for Cohort 4

- During the OLE period at Visit 8 (Week 16 for Cohorts 1& 2 or Week 14 for Cohort 3 or Week 12 for Cohort 4), Visit 11 (Week 28 for Cohorts 1& 2 or Week 26 for Cohort 3 or Week 24 for Cohort 4), Visit 13 (Week 52 for Cohorts 1& 2 or Week 50 for Cohort 3 or Week 48/ end of OLE period for Cohort 4), Visits 15, 17, 19 (every 24 weeks) and Visit 20 (Week 130/ end of OLE period for Cohorts 1 to 3 or early termination during OLE period for all cohorts).

ADA measurements will be assigned to the same analysis windows as defined for efficacy endpoints ([Table 3](#) and [Table 4](#)).

The following variables will be described for both OLDFI period and the OLDFI/OLE combined period:

- ADA response (Positive or Negative).

For ADA positive:

- Titer levels
- Neutralizing status (Positive or Negative)
- Pre-existing positive ADA defined as patients with positive ADA response at baseline with less than 4-fold increase in titer in the post-baseline period
- Treatment-emergent positive ADA response defined as
 - Patients with no ADA positive response at baseline but with any positive response in the post-baseline period (for OLDFI period: up to follow-up visit, for the OLDFI/OLE combined period: up to end of OLE period); OR
 - Patients with a positive ADA response at baseline and at least a 4-fold increase in titer in the post-baseline period (for OLDFI period: up to follow-up visit, for the OLDFI/OLE combined period: up to end of OLE period).
 - For treatment-emergent positive ADA, the following categories for ADA duration will be applied for the analysis performed on the OLDFI/OLE combined period:
 - A persistent positive response is a treatment-emergent ADA positive response detected in at least 2 consecutive post-baseline samples separated by at least a 12-week period
 - An indeterminate duration positive response is defined as ADA present only at the last sampling time point
 - A transient positive response is defined as any treatment-emergent positive ADA response that is neither considered persistent nor indeterminate

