In addition, potential ADA samples to be collected in case of ADA titer ≥ 240 at the last measurement for patients not entering to the OLE phase, or for patients proceeding into OLE phase but not entering into the Phase 3 study will be listed.

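### Cohort 4 patients who complete the main phase but skip the extension have no scheduled antibody sample at the Week 12 point that triggers long-term antibody follow-up

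*Protocol*

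**What the plan says.** **The trigger.** Protocol 8.3.3 covers patients who stop the main phase early or do not enter the extension. Those with a titer of 240 or more at the follow-up visit (Cohorts 1-3) "or at the end of the dose finding treatment period (for Cohort 4) will have additional antibody sample(s"), first at 6 to 12 months and then about every 3 to 6 months until the titer falls below 240. Protocol 9.3.1.1 uses the same time point: "end of dose finding treatment period (Cohort 4) / end of extension phase will have additional antibody sample(s").

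**When dose finding ends for Cohort 4.** The heading of Protocol 10.1.2.7 is "Visit 8/Week 12 (end of the OL dose finding treatment period) (Cohort 4 only"). The notes to the Cohort 4 design figure (1.1.2) and SAP 2.5.3 also give Week 12.

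**Dosing.** Protocol 1.1.2: "The main phase for Cohort 4 will include 3 alirocumab injections (at W0, W4, and W8").

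**Sampling.** The row "Anti-alirocumab antibodies (ADA") in the Cohort 4 main-phase flow chart (1.3.2) carries two marks, Week 0 and Week 8. Footnote l of that chart and section 9.3.1.1 require sampling before the injection.

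**The flow-chart footnote.** Footnote m of 1.3.2 ties extra sampling to a different visit: patients who "have a titer at or above 240 for ADA at follow-up visit will have additional ADA samples". Protocol 8.1.2 and 10.1.3 give Cohort 4 no follow-up period.

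**The SAP.** Section 2.1.4.8 adds "and Week 12 for Cohort 4" to the ADA time points of the dose-finding period. It also says that extra samples prompted by a titer of 240 or more "at the last measurement for patients not entering to the OLE phase" will be listed.

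**The concern.** A follow-up rule that depends on a titer needs a sample at the stated time. For one planned route through Cohort 4 there is none. A patient who finishes Week 12 and then declines the extension, or moves directly to Phase 3, was last sampled for ADA just before the third and final dose.

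Two things are at stake. First, the site and sponsor cannot apply the long-term sampling rule to these patients as written, although the development of antibodies is a secondary objective and Section 4 names immunogenicity as an identified risk. Second, the SAP places all of Cohort 4 in one ADA population and summarizes results by time point. In that summary, some completers have two post-baseline samples and others one, and which they have depends on whether they entered the extension. Cohort 4 has the highest Q4W doses in the study.

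**Working it through.** No sample-size or error-rate figure is involved. The check sets the schedule beside the rule.

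**1. Which samples exist for Cohort 4 in the main phase?** The flow chart shows two ADA marks. Some late columns of the laboratory table are out of line in the extracted text, so the visit lists carry the weight:
- Week 0 (10.1.2.1): ADA listed.
- Week 4 (10.1.2.3): no ADA.
- Week 8 (10.1.2.5): ADA listed; the third injection is given at this visit.
- Week 10 (10.1.2.6): lipids and PK/PCSK9 only.
- Week 12 (10.1.2.7): lipids, PK/PCSK9 and a urine pregnancy test; no ADA.

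The flow chart and the visit lists agree: Week 0 and Week 8 only.

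**2. How does the last sample relate to dosing?** Injections are on nominal days 0, 28 and 56. The Week 8 sample is taken on day 56, before dosing.
- Injections before the last ADA sample: 2 of 3.
- Time since the second injection: 56 − 28 = 28 days.
- The trigger point is Week 12, day 84. Time since the third injection: 84 − 56 = 28 days. No ADA is drawn then under the main-phase schedule.

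**3. Who is affected?** Scheduled or required ADA samples after the last main-phase injection:

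| Group | Sample after the last injection | Source |
|---|---|---|
| Cohorts 1 and 2 | Week 16: 16 − 6 = 10 weeks after it | 1.3.1, 10.1.3.2 |
| Cohort 3 | Week 14: 14 − 4 = 10 weeks after it | 1.3.1, 10.1.3.2 |
| Cohort 4, entering the extension | Week 12: 12 − 8 = 4 weeks after it | 1.4.2 |
| Cohort 4, stopping treatment early | Unscheduled visit, 28 to 35 days after it | 10.3.4 |
| Cohort 4, completing but not entering the extension | None | 1.3.2, 10.1.2.7 |

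Only the last row has a gap. Those patients have one post-baseline ADA sample (Week 8); extension entrants have two (Weeks 8 and 12).

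**4. Do the other passages agree?** No. Protocol 8.3.3 and 9.3.1.1 use the end of dose finding. Footnote m uses a follow-up visit that Cohort 4 does not have. SAP 2.1.4.8 counts Week 12 as a dose-finding sample, but the protocol schedules it only through the extension. The SAP also runs the dose-finding definition of treatment-emergent ADA up to the follow-up visit, which again does not exist for Cohort 4.

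**The case against.** Several points on the other side are sound.

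- **Early stoppers are covered.** A reader might infer that every Cohort 4 patient outside the extension lacks a sample after the last dose, or that the trigger fails for everyone it was written for. The documents do not support that. Section 8.3.3 also names patients who discontinue early, and 10.3.4 requires ADA from those who stop treatment, 28 to 35 days after the last injection. Section 10.6.2.1 further calls for unscheduled ADA after allergic skin events or worsening injection-site reactions.
- **The short Week 12 draw is deliberate.** Section 4 limits Week 10 and Week 12 measurements to reduce blood volume in children, and an ADA sample is 5 mL (9.3.1.2). This stands, so an added tube has a real cost. It does not resolve the conflict: if ADA was left out on purpose, 8.3.3 and 9.3.1.1 cannot rely on a Week 12 titer and the SAP cannot list one.
- **The SAP already uses the last measurement.** That sentence says which extra samples will be listed. It is a reporting rule and should not be read as a sampling trigger.
- **Week 8 could be the end of dose finding.** The heading of 10.1.2.5 says so without naming a cohort. For Cohort 4, 1.1.2, 10.1.2.7 and SAP 2.5.3 say Week 12. If Week 8 was intended, the text still needs correcting, and the titer would still precede the third dose.
- **It is small.** The group may be empty, and ADA results are descriptive. No primary efficacy estimate depends on them.

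**Conclusion.** The inconsistency is real and narrow. For Cohort 4 patients who complete the main phase and do not enter the extension, the antibody follow-up rule refers to a titer that the protocol does not schedule. They have no scheduled ADA sample after the third injection, and the SAP expects one that will not exist for them. The group's size is not stated; within a cohort of about 10 it lies between 0 and about 10. Not entering the extension is a planned route, because patients may decline or go directly to Phase 3.

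This rests on Week 12 being the end of dose finding for Cohort 4 and on the visit lists in 10.1.2.5 to 10.1.2.7 being complete. It does not extend to extension entrants or to patients who stop treatment early and attend the visit in 10.3.4, and it leaves the primary endpoint untouched. It is an error in the text as it stands, not merely missing detail, and should be corrected.

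**What to change.** Reconcile Protocol 1.3.2 (ADA row and footnote m), 8.3.3, 9.3.1.1 and 10.1.2.7 with SAP 2.1.4.8, so that the trigger names a sample that is collected. There are two consistent ways to do this:

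1. **List ADA at the Week 12 draw for all Cohort 4 patients** in 1.3.2 and 10.1.2.7, and point footnote m to that visit. All completers then have a titer 28 days after the third injection, and the SAP list is correct. The cost is one 5 mL tube for completers outside the extension, at a visit where blood is already taken. This must be weighed against the Section 4 aim of limiting blood volume.
2. **Tie the trigger to the last available main-phase sample** in 8.3.3, 9.3.1.1 and footnote m, and remove Week 12 from SAP 2.1.4.8 for patients not entering the extension. This costs wording only. It does not supply a titer after the third dose, so the SAP and the report should say that treatment-emergent ADA in these patients rests on one post-baseline sample taken before that dose.

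Under either option, SAP 2.1.4.8 should replace the follow-up visit as the end of the dose-finding ADA period for Cohort 4, and the report should give the number of Cohort 4 completers who did not enter the extension.

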8.3.4 Committee

The DMC will receive unblinded lipid parameter results and confidential reports ([Section 6.4](#)).

8.4 METHOD OF ASSIGNING PATIENTS TO TREATMENT GROUP

The list of treatment kit number will be generated centrally by Sanofi. The IMP (Cohorts 1 & 2 (Q2W) or Cohort 3 (Q4W), body weight less than 50 kg or greater or equal to 50 kg) will be packaged in accordance with this list. The below table represents the allocation according to the doses/ dose regimen:

Table 1 - Allocation according to the doses/dose regimen for dose-finding treatment period and extension period until PFS will be available

	30 mg Q2W	40 mg Q2W	50 mg Q2W	75 mg Q2W	75 mg Q4W	150 mg Q4W
Solvent for alirocumab vial	1	2	1	0	1	0
150 mg vial	1	1	1	1	1	1

The Trial Supply Operations Manager (TSOM) will provide the list of treatment kit numbers. Then, this centralized treatment allocation system provider will generate the patient list according to which it will allocate the treatment kits to the patients.

Patients will be allocated to receive repeated dose of SC alirocumab injections administered every 2 weeks (Q2W) or every 4 weeks (Q4W) in 4 independent cohorts of children and adolescents aged 8 to 17 years. Each independent cohort below will include up to 10 patients with no less than 4 patients in each BW category:

- Cohort 1 will receive 30 mg Q2W for body weight (BW) <50 kg and 50 mg Q2W for BW \geq 50 kg.
- Cohort 2 will receive 40 mg Q2W for BW <50 kg and 75 mg Q2W for BW \geq 50 kg.
- Cohort 3 will receive 75 mg Q4W for BW <50 kg and 150 mg Q4W for BW \geq 50 kg.

- Cohort 4 will receive 150 mg Q4W for BW <50 kg and 300 mg Q4W for BW \geq 50 kg.

For Cohorts 1 & 2: The treatment kit numbers will be allocated using the centralized treatment allocation system on visit 2 (Day 1, Week 0 to Week 6 according to the cohort and the body weight: main treatment period), and then at Week 16 according to the cohort (open label dose finding treatment period) and every 3 months (open label extension treatment period) when PFS are available or every 2 weeks if PFS are not available as resupply visits, and at unscheduled visits, if needed.

For Cohort 3: The treatment kit numbers will be allocated using the centralized treatment allocation system on visit 2 (Day 1, Week 0 and second injection, Week 4 according to the body weight: main treatment period), and then at Week 14 (open label dose finding treatment period) and every 3 months (open label extension treatment period) when PFS are available or every 4 weeks if PFS are not available as resupply visits, and at unscheduled visits, if needed.

For Cohort 4: The treatment kit numbers will be allocated using the centralized treatment allocation system on visit 2 (Day 1, Week 0 and second injection, Week 4 according to the body weight: main treatment period, with third injection, Week 8), and then at Week 12 (open label dose finding treatment period) and every 3 months (open label extension treatment period).

Before allocating a treatment kit to the patient, the investigator or designee will have to contact the centralized treatment allocation system.

An included patient is defined as a patient who is registered and assigned with a treatment kit number from the centralized treatment allocation system, as documented from its log file regardless of whether the treatment kit will be used or not. A patient cannot be included more than once in the study. If a treatment is used without contacting the centralized treatment allocation system, then the patient will be considered as not included and withdrawn from the study.

Two types of centralized treatment allocation system will be used, the Interactive Voice Response System (IVRS) and the Interactive Web Response System (IWRS) depending on the choice of the site. Interactive response technology (IRT) covers both centralized treatment allocation.

